3.8.7 Subgroup Analyses

The treatment emergent AEs and SAEs will be summarized by 4-gene IFN signature (IFN high vs IFN low) and ADA status (positive vs negative).

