 - Urine β-HCG (dipstick; females of childbearing potential only, ensure result is negative)
- 4. Assess worsening and/or flare of SLE disease activity using SLE Increase in Disease Activity CRF and complete for SLE related AEs that are not serious, if applicable
- 5. Evaluate subject for signs and symptoms of TB using a TB surveillance form
- 6. Take vital signs before administration of investigational product (within 15 minutes of the beginning of the investigational product infusion)
- 7. Administer investigational product
 - Take vital signs (BP, pulse, respiration, and temperature) approximately every 15 (± 5) minutes during the infusion, immediately after completion of the infusion, approximately 30 (± 5) and 60 (± 5) minutes after completion of administration of

investigational product, and every 30 (\pm 5) minutes thereafter or until stable and ready for discharge (as judged by the investigator)

8. Assess for AEs/SAEs/AESIs (nonserious AEs will only be captured during the first year of the subject's participation in the study; however, nonserious AEs that result in interruption of investigational product and/or discontinuation from the study will be captured at any time during the subject's participation in the study)

5.1.2.3 Every 12 Weeks; Weeks 12, 24, 36, 48, 60, 72, 84, 96, 108, 120, 132, and 144 (Visits 4, 7, 10, 13, 16, 19, 22, 25, 28, 31, 34, and 37)

In addition to procedures and assessments performed Q4W, the following are to be performed **every 12 weeks (Q12W)**:

- 1. Collect **predose** blood samples for:
 - Serum chemistry
 - Hematology
 - QuantiFERON-TB Gold (QFT-GIT; TB testing, only if indeterminate at any visit during Study CD-IA-MEDI-546-1013)
 - SLEDAI-2K-associated lab tests (C3, C4, CH50, anti-dsDNA)
 - Pharmacokinetics (MEDI-546 serum concentration; Weeks 12, 24, 36 and 48 only)
 - Pharmacodynamics (type I IFN signature with 21-gene assay; Weeks 12, 24, 36 and 48 only)
 - Immunogenicity (ADA to MEDI-546; Weeks 12, 24, 36 and 48 only)
 - Proteomics/biomarkers (Weeks 12, 24 and 48 only; optional)
- 2. Collect urine sample for:
 - Urinalysis
 - SLEDAI-2K-associated lab tests: urine protein/creatinine ratio
 - Urine biomarker (optional)
- 3. Perform SLEDAI-2K

5.1.2.4 Every 24 Weeks; Weeks 24, 48, 72, 96, 120 and 144 (Visits 7, 13, 19, 25, 31, and 37)

- 1. Administer SF-36v2 (should be completed prior to any clinical assessments)

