- 2. Immunology profile (ANA, extractable nuclear antigens [RNP, Sm, SSA, SSB], quantitative immunoglobulins)
- 3. Perform SLICC/ACR Damage Index

In addition to procedures and assessments performed Q4W, the following are to be performed every 24 Weeks (Q24W) starting at Week 72:

- 4. Collect **predose** blood samples for:
 - Pharmacokinetics (MEDI-546 serum concentration)
 - Pharmacodynamics (type I IFN signature with 21-gene assay)
 - Immunogenicity (ADA to MEDI-546)
 - Proteomics/biomarkers (optional)

5.1.2.5 Every 48 Weeks; Weeks 48, 96, and 144 (Visits 13, 25, and 37)

In addition to procedures and assessments performed Q4W, the following are to be performed every 48 weeks (Q48W) starting at Week 48:

- 1. Record weight
- 2. Assess for Cushingoid features
- 3. Perform Papanicolaou (Pap) smear examination in females only (only at Visit 37, Week 144)
- 4. Perform ECG
- 5. Collect blood samples for:
 - Lipid profile (Subjects will be required to fast for at least 8 hours prior to this assessment. If a subject has not fasted, the assessment should be performed under fasted conditions at the next visit)
 - Immunology profile (ANA, extractable nuclear antigens [RNP, Sm, SSA, SSB], quantitative immunoglobulins)

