7.3.2 Secondary Endpoint

The secondary objective of this study is to evaluate the IM of MEDI-546. Immunogenicity results will be analyzed by summarizing the number and percentage of subjects who develop detectable ADAs. The titer of ADAs will also be summarized. The association of ADA titers with AEs, PK, SLEDAI-2K, and PD markers will also be evaluated.

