3.6 Pharmacodynamic Endpoint and Analyses

3.6.1 Type I IFN Signature

The 21-gene type I IFN signature in whole blood will be used as a PD marker. The gene signature and the neutralization levels will be summarized by visit. Subgroup analysis of 21-gene type I IFN signature will be performed based on ADA status (positive vs negative).

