3.8.4 Exposure Adjusted Adverse Events Rate

The exposure adjusted rate (per 100 patient-year) for treatment emergent AEs, non-serious AEs, acute AEs, investigational product related AEs, AEs by highest severity, AEs leading to treatment discontinuation, AEs resulting in death, SAEs and AESIs will be summarized. The exposure adjusted subject rate per 100 patient-years is defined as [the number of subjects with an event/(total exposure time in days/365.25)]*100.

For treatment emergent AEs leading to treatment discontinuation, AEs resulting in death, SAEs and AESIs, duration of exposure is calculated as follows:

- Anifrolumab Total group: duration of exposure (days) = minimum(end of study date in CD1145, last dosing date in CD1145+85 days) – first dosing date in CD1145+1.

- Anifrolumab 1000 mg group:
 - For subjects who received 1000 mg only during the study: duration of exposure (days) = minimum(end of study date in CD1145, last dosing date in CD1145+85 days) – first dosing date in CD1145+1.
 - For subjects who received both 1000 mg and 300 mg during the study: duration of exposure (days) = (first dosing date of 300 mg – 1) – first dosing date in CD1145 + 1.
- Anifrolumab 300 mg group: duration of exposure (days) = minimum(end of study date in CD1145, last dosing date in CD1145+85 days) – first dosing date of 300 mg +1.

The AEs leading to treatment discontinuation, AEs resulting in death, SAEs and AESIs occurred during the exposure period will be included in the summary.

The non-serious AEs are captured during the first year of subject's participation only. So for treatment emergent AEs, non-serious AEs, acute AEs, investigational product related AEs, and AEs by highest severity, duration of exposure is calculated as follows:

- Anifrolumab Total group: duration of exposure (days) = minimum(end of study date in CD1145, first dosing date in CD1145+364) – first dosing date in CD1145+1.
- Anifrolumab 1000 mg group:
 - For subjects who received 1000 mg only during the study: duration of exposure (days) = minimum(end of study date in CD1145, first dosing date in CD1145+364) – first dosing date in CD1145+1.
 - For subjects who received both 1000 mg and 300 mg during the study: duration of exposure (days) = minimum(first dosing date in CD1145+364, first dosing date of 300 mg-1) – first dosing date in CD1145 + 1.
- Anifrolumab 300 mg group: minimum(end of study date in CD1145, first dosing date in CD1145+364) - first dosing date of 300 mg +1.

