3.9 Immunogenicity

The IM results will be analyzed by summarizing the number and percentage of subjects who develop positive ADA. A descriptive summary of actual ADA titers by visit will also be provided.

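### AEs and SAEs are split by ADA status with no rule tying event onset to the first positive ADA sample, so events before seroconversion can be counted as ADA-positive events

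*SAP*

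**What the plan says.** - **The table at issue (SAP 3.8.7).** "The treatment emergent AEs and SAEs will be summarized by 4-gene IFN signature (IFN high vs IFN low) and ADA status (positive vs negative". The section says nothing more about ADA.
- **ADA classification (SAP 3.9).** The only other classification is "the number and percentage of subjects who develop positive ADA". The section adds: "A descriptive summary of actual ADA titers by visit will also be provided". Neither is connected to when an event began.
- **Same label for PD (SAP 3.6.1).** "Subgroup analysis of 21-gene type I IFN signature will be performed based on ADA status (positive vs negative".
- **Protocol commitment (7.3.2).** "The association of ADA titers with AEs, PK, SLEDAI-2K, and PD markers will also be evaluated". No method is given.
- **ADA sampling.** Samples are taken on Day 1 (Protocol 5.1.2.1). Section 5.1.2.3 then lists "Immunogenicity (ADA to MEDI-546; Weeks 12, 24, 36 and 48 only", and Section 5.1.2.4 has samples "performed every 24 Weeks (Q24W) starting at Week 72". Further samples follow at Week 156 (5.1.2.6) and 28 and 85 days after the last dose (5.1.3.1, 5.1.3.3).
- **AE capture.** SAP 3.8.4 states: "The non-serious AEs are captured during the first year of subject's participation only". Protocol 6.1.1 excepts non-serious events that interrupt dosing or lead to discontinuation. SAEs and AESIs are captured throughout.
- **Exposure adjustment.** SAP 3.2.2 and 3.8.4 plan exposure-adjusted rates by dose and in total, not by ADA status. The ADA table therefore rests on crude numbers and percentages.

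**The concern.** ADA status can change at any sample over about 168 weeks, but the table uses one fixed label per subject. If the label means ever positive, an event in month 2 of a subject who first tests positive in month 30 is shown as an event in an ADA-positive subject. ADA cannot have contributed to it in the sense the table suggests.

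The mismatch is sharpest for non-serious AEs. Most are collected in year 1 only, while ADA is looked for until 85 days after the last dose. SAP 3.8.4 recognises this and cuts exposure at 365 days for the categories that include non-serious events. Section 3.8.7 has no such rule.

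This is the only analysis visible in the SAP that addresses the protocol's stated association of ADA with AEs. If the positive column mixes events from before and after seroconversion, a true effect is diluted and an absent effect cannot be shown cleanly.

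**Working it through.** **The plan's own figure.** The documents give no figure for this table. The stated size (SAP 2.4) reproduces: 307 × (1 − 0.20) = 245.6, against approximately 240.

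**Step 1: hand check without dropout.** Assume a constant SAE rate unrelated to ADA. The share of a converter's SAEs that precede the first positive sample is then (mean day of first positive) / (days followed). Full follow-up is 156 × 7 + 85 = 1,177 days. On-treatment samples after Day 1 fall on days 84, 168, 252, 336, 504, 672, 840, 1,008 and 1,092. Onset is assumed uniform over an interval, and each onset is detected at the next sample.

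- Onset within 168 days: mean = (84 + 168)/2 = 126, and 126/1,177 = 10.7%.
- Onset within 365 days: mean = [84 × (84 + 168 + 252 + 336) + 29 × 504]/365 = 233, and 233/1,177 = 19.8%.
- Onset within 1,092 days: mean = [84 × 840 + 168 × (504 + 672 + 840 + 1,008) + 84 × 1,092]/1,092 = 614, and 614/1,177 = 52.2%.

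**Step 2: simulation with dropout.** Each scenario has 400,000 to 600,000 subjects, the protocol's sampling days, four-weekly dosing to Week 156, 85-day follow-up, status taken as ever positive, and no ADA effect on SAEs. The following values are assumed and are not in the documents:

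- ADA incidence of 5-20% over three years
- SAE rate of 5-20 per 100 patient-years
- dropout of 5-20% per year
- 0% or 3% positive at Day 1
- dropout hazard unchanged or doubled after ADA

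| Assumed ADA onset | SAEs in positives before first positive | Year-1 time of positives before first positive | First positive after year 1 |
|---|---|---|---|
| within 24 weeks | 11-17% | 35-37% | 0% |
| within 1 year | 21-30% | 61-62% | 7-8% |
| over 3 years, none positive at Day 1 | 52-58% | 84-87% | 61-69% |
| over 3 years, 3% positive at Day 1 | 42% | 65% | 50% |

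The hand figures sit at or just below each range, as they should, because dropout shortens the denominator.

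**Step 3: follow-up.** This is the ratio of the percentage with an SAE, ever-positive over negative (true value 1.0), with none positive at Day 1.

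| Assumed ADA onset | Dropout unrelated to ADA | ADA doubles dropout |
|---|---|---|
| within 24 weeks | 1.01-1.02 | 0.84-0.95 |
| within 1 year | 1.01-1.07 | 0.91-0.97 |
| over 3 years | 1.04-1.19 | 1.03-1.11 |

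**Step 4: splitting time at the first positive sample.** Counting SAEs per person-time before versus from that sample gives a rate ratio of 0.96-1.03 with onset over three years and dropout unrelated to ADA.

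**Step 5: scale in this study.** Take 240 subjects, 10% ADA over three years, SAEs at 10 per 100 patient-years and 10% dropout per year. About 9.3% are ever positive: 240 × 0.093 = 22 subjects. Their follow-up is 22.3 × 3.035 = 68 patient-years, giving 6.8 expected SAEs. Of these, 55.1%, or 3.7, precede the first positive sample. The remaining person-time is 68 × 0.449 = 30 patient-years, with about 3 SAEs.

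**Step 6: a caution on the rate formula.** SAP 3.8.4 divides subjects having an event by all exposure and does not stop the clock at the first event, so longer segments read lower. At 10 per 100 patient-years, a 1.36-year segment (3.035 × 0.449) gives 100 × (1 − e^−0.136)/1.36 = 9.35. A 2.76-year segment gives 100 × (1 − e^−0.276)/2.76 = 8.74. The ratio is 1.07 with no true effect. The ratios in Step 4 count events, which avoids this.

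**The case against.** **The status may mean Day 1 status.** In the same sentence it is paired with the 4-gene signature, a one-time Day 1 measure that SAP 3.3.2 lists among baseline characteristics. Under that reading neither consequence follows. SAP Section 1 also places table specifications in a separate programming plan, which may hold a definition. This stands to the extent that ever-positive is inferred and not stated. A reader might infer that the SAP prescribes a biased comparison; it prescribes an undefined one. Day 1 status alone would not serve either. Everyone who seroconverts in this study would be counted as negative, although immunogenicity during the study is the secondary objective.

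**The follow-up argument is weak.** A reader might infer that longer-followed subjects are over-represented among positives. The documents do not support that as a general statement. The effect is close to nil with early onset and reverses if ADA drives discontinuation. Even with onset over three years it is small: in the Step 5 scenario, 26.1% against 23.9% is 2.2 points, about half a subject among 22. The standard error of the positive-group percentage is √(0.261 × 0.739/22.3) = 9 points. What stands is that follow-up may differ in either direction and is not adjusted for.

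**The table is descriptive.** Protocol 7.3.1 rules out formal testing, and subject listings are planned (SAP 3.1). This stands, and it limits the point to interpretation.

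**Time-split data will be sparse.** This is true: about 30 positive patient-years and 3 SAEs in the Step 5 scenario. The unsplit table looks fuller only because it includes events from before seroconversion.

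**Conclusion.** The point holds in this form: Section 3.8.7 leaves ADA status undefined and has no timing rule. Under the natural ever-positive reading, events before seroconversion are counted as ADA-positive events. The direction of this misattribution does not depend on the assumptions; its size does. Roughly 11-58% of SAEs in positives precede the first positive sample, and 35-87% of their year-1 time does, according to how early ADA appears. No single percentage should be quoted without its onset assumption, because the documents give no ADA, SAE or dropout rates for this study. Subjects already positive at Day 1 have no pre-conversion events. They are possible because two of the three parent-study arms received anifrolumab (SAP 2.2).

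No primary result or test depends on the table. The change is worth making because this is the only visible SAP analysis of ADA against AEs and the data needed are already collected.

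**What to change.** 1. In SAP 3.8.7, define ADA status with three groups: positive at OLE Day 1, becoming positive in the OLE, and never positive.
2. Tabulate AEs and SAEs in person-time before versus from the first positive sample, with exposure-adjusted rates on the 3.8.4 formula. Never-positive subjects contribute negative time only. SAP 3.8.4 already divides a subject's exposure at the first 300 mg dose, so the programming pattern exists. Given Step 6, show events per 100 patient-years alongside.
3. For non-serious AEs, apply the same before/from split within the year-1 window. Restricting to year-1 ADA samples without the split would not be enough: with onset inside one year, 35-62% of positives' year-1 time still precedes the first positive sample.
4. Do not rely on Day 1 status alone.
5. In SAP 3.6.1, refer to the same ADA definition. That summary is by visit, so it needs nothing further.

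The cost is SAP wording and one more descriptive table, with no new data. ADA-positive person-time will be sparse, so the table should show the number of subjects and patient-years in each column.

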3.2 Estimated Duration of Subject Participation

Subjects will be in this study for approximately 168 weeks (156 weeks for treatment and 12 weeks for follow-up).

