Subjects who are permanently discontinued from receiving investigational product will be followed for safety per Section 6.4, including the collection of any protocol-specified blood or urine specimens, unless consent is withdrawn or the subject is lost to follow-up or enrolled in another clinical study. Twenty-eight days (\pm 7 days) after the last dose of investigational product, subjects will begin the follow-up period by completing the Visit 41/Early Discontinuation Visit assessments. Two subsequent follow-up visits will also be completed 59 and 85 days (\pm 7 days) after the last dose of investigational product as per the schedule of study procedures. A subject who receives any SLE medication or SLE treatment listed in Appendix 3 (other than those prohibited medications or treatments listed above) may be allowed to continue receiving investigational product only if permission from the sponsor is obtained.

Concomitant medications that require the sponsor to be notified immediately and the medical monitor to be consulted to determine if a subject may continue to receive investigational product include, but are not limited to:

- Corticosteroids with a long biologic half-life (eg, dexamethasone, betamethasone)
- Increase in oral corticosteroids (OCS) treatment above a total dose > 40 mg/day for a dosing period > 14 days, dosing with MEDI-546 may be continued, unless there is a safety concern. However, it should be noted that frequent steroid use above Study CD-IA-MEDI-546-1013 baseline for SLE disease control (> 2 times every 6 months, higher doses [> 40 mg/day], and/or longer duration than permitted by the protocol) after 12 months of open-label MEDI-546 should result in discontinuation of MEDI-546 administration for failure to achieve a favorable benefit:risk profile.

Withdrawal of consent: If consent is withdrawn, the subject will not receive any further investigational product or further study observation. Note that the subject may need to undergo additional tests or tapering of treatment to withdraw safely.

Lost to follow-up: Subjects will be considered lost to follow-up only if no contact has been established by the time the study is completed (as defined in Section 4.9) such that there is insufficient information to determine the subjects' status as of their last visit.

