3.2.2 Treatment Groups for Analysis

Treatment group is Anifrolumab Total for all analyses except the exposure adjusted adverse event which will be summarized by Anifrolumab 300 mg, Anifrolumab 1000mg, and Anifrolumab Total.

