3.8 Safety Analyses

3.8.1 Adverse Events and Serious Adverse Events

Adverse events (AEs) will be coded by MedDRA version 18.0 or higher and the type incidence, severity and relationship to study investigational product will be summarized. Specific adverse events will be counted once for each subject for calculating percentages. In addition, if the same AE occurs multiple times within a particular subject, the highest severity and level of relationship observed will be reported. All treatment-emergent AEs will

be summarized overall, as well as categorized by MedDRA System Organ Class and Preferred Term.

The acute AEs are defined as events that occur within a 24 hour period after dosing. The acute AEs will be summarized.

The treatment-emergent non-serious AEs will also be summarized.

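### SAP 3.8.7 would show SAEs by IFN-high and IFN-low as crude percentages, so any difference in retention between the two groups would appear as a difference in SAE frequency

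*SAP*

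**What the plan says.** SAP 3.8.7 consists of one sentence: "The treatment emergent AEs and SAEs will be summarized by 4-gene IFN signature (IFN high vs IFN low) and ADA status (positive vs negative". It does not say whether the summary is a percentage or a rate.

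The general rule for adverse events, in SAP 3.8.1, is "Specific adverse events will be counted once for each subject for calculating percentages".

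SAP 3.8.4 has an exposure-adjusted measure: "The exposure adjusted subject rate per 100 patient-years is defined as [the number of subjects with an event/(total exposure time in days/365.25)]*100". It uses a full-period window (to the earlier of end of study and last dose plus 85 days) for SAEs, AESIs, deaths and discontinuations. It uses a first-year window for TEAEs overall and for non-serious events. SAP 3.2.2 says where the measure applies: "Treatment group is Anifrolumab Total for all analyses except the exposure adjusted adverse event which will be summarized by Anifrolumab 300 mg, Anifrolumab 1000mg", and the Total column. Nothing extends it to the IFN or ADA subgroups.

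On time observed, Protocol 3.2 gives "Subjects will be in this study for approximately 168 weeks (156 weeks for treatment and 12 weeks for follow-up". There is no minimum, because under Protocol 4.2.3 "If consent is withdrawn, the subject will not receive any further investigational product or further study observation". Protocol 6.1.1 captures SAEs and AESIs throughout participation. Non-serious AEs are captured in the first year only, except AESIs and events that lead to interruption of drug or discontinuation.

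The 4-gene IFN test is a single Day 1 sample (Protocol 5.1.2.1), so IFN status is a true baseline grouping.

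**The concern.** A percentage that counts each subject once rises with the time that subjects are watched. When follow-up ranges from weeks to more than three years, two groups with the same SAE rate but different retention will show different SAE percentages.

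The documents give one route by which retention could differ with IFN status. After 12 months of open-label drug, frequent steroid use for disease control "should result in discontinuation of MEDI-546 administration for failure to achieve a favorable benefit:risk profile" (Protocol 4.2.3). Observation then ends about 85 days after the last dose (Protocol 4.2.3 and 4.7). The drug acts on type I IFN signalling (Protocol 1.3), and Protocol 1.1 associates a high IFN signature with greater disease activity. IFN status could therefore bear on disease control, and so on time in the study. The direction is not known.

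Safety is the primary objective and is reported entirely through descriptive tables. A side-by-side SAE percentage by IFN status, without patient-years, gives the reader no means of separating risk from length of stay. A real excess in the group that leaves earlier could also be understated.

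**Working it through.** **Plan's own figures.** The plan states no number for this summary. The maximum follow-up reproduces: 156 + 12 = 168 weeks, and 168 × 7 / 365.25 = 3.22 years. One dose plus 85 days is 86 / 365.25 = 0.24 years. Withdrawal of consent at four weeks is 28 / 365.25 = 0.08 years.

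**Assumed inputs (none is in the documents).** The SAE rate h is equal in both groups at 0.05, 0.10 or 0.20 per year. Dropout d is a constant yearly rate of 0.10 against 0.20, 0.10 against 0.30, or 0.15 against 0.30. T = 3.22 years.

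**Formulas.**
- Crude proportion with an SAE: C(h, d, T) = h/(h+d) × (1 − exp(−(h+d)T)).
- Mean follow-up: F(d, T) = (1 − exp(−dT))/d.
- SAP 3.8.4 rate per 100 patient-years: 100 × C/F.
- Divergence only after month 12: both groups have the lower dropout d1 in year 1, and the shorter-stay group then has d2. Its crude proportion is C(h, d1, 1) + exp(−(h+d1)) × C(h, d2, T−1).

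**One case in full: h = 0.10, dropout 0.10 against 0.30.**
- Longer-stay group: 0.5 × (1 − exp(−0.644)) = 23.7%; mean follow-up 2.75 years; SAP 3.8.4 rate 8.62.
- Shorter-stay group, divergence from Day 1: 0.25 × (1 − exp(−1.288)) = 18.1%; mean follow-up 2.06 years; rate 8.77. The crude ratio is 1.31 and the rate ratio 0.98.
- Shorter-stay group, divergence after month 12: 0.0906 + 0.8187 × 0.1471 = 21.1%; mean follow-up 2.42 years; rate 8.73. The crude ratio is 1.12 and the rate ratio 0.99.

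**All cases (longer-stay against shorter-stay, no true difference).**

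| SAE rate per 100 PY | Dropout per year | Crude %, from Day 1 | Crude ratio | SAP 3.8.4 rate ratio | Crude %, after month 12 | Crude ratio |
|---|---|---|---|---|---|---|
| 5 | 10% v 20% | 12.8 v 11.1 | 1.15 | 1.00 | 12.8 v 12.0 | 1.07 |
| 5 | 10% v 30% | 12.8 v 9.7 | 1.32 | 0.99 | 12.8 v 11.3 | 1.13 |
| 5 | 15% v 30% | 11.9 v 9.7 | 1.23 | 0.99 | 11.9 v 10.8 | 1.09 |
| 10 | 10% v 20% | 23.7 v 20.6 | 1.15 | 0.99 | 23.7 v 22.3 | 1.06 |
| 10 | 10% v 30% | 23.7 v 18.1 | 1.31 | 0.98 | 23.7 v 21.1 | 1.12 |
| 10 | 15% v 30% | 22.1 v 18.1 | 1.22 | 0.99 | 22.1 v 20.3 | 1.09 |
| 20 | 10% v 20% | 41.3 v 36.2 | 1.14 | 0.98 | 41.3 v 39.1 | 1.06 |
| 20 | 10% v 30% | 41.3 v 32.0 | 1.29 | 0.97 | 41.3 v 37.1 | 1.11 |
| 20 | 15% v 30% | 38.6 v 32.0 | 1.21 | 0.98 | 38.6 v 35.8 | 1.08 |

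For divergence after month 12, the SAP 3.8.4 rate ratio is 0.98 to 1.00. With equal dropout every ratio is 1.00. With a narrower gap of 15% against 20% from Day 1, the crude ratio is about 1.07.

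**Masking.** Suppose the shorter-stay group truly has a 25% higher rate (12.5 against 10), with dropout 30% against 10%. With divergence from Day 1, the crude figures are 21.9% against 23.7%, the wrong direction, while the SAP 3.8.4 rates are 10.6 against 8.6. With divergence after month 12, the crude figures are 25.5% against 23.7%, a ratio of 1.08 where the truth is 1.25.

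**TEAEs.** In a one-year window with assumed TEAE rates of 50 to 200 per 100 patient-years and the same dropout pairs from Day 1, the crude ratio is 1.03 to 1.09. If retention diverges only after month 12, the first-year data are unaffected.

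**The case against.** **The SAP is silent, not explicitly unadjusted.** SAP 3.8.7 says only that events are summarized, and table templates sit in a separate programming plan (SAP 1) that is not available. A reader might infer that the SAP plans a formal comparison of risk by IFN status. It does not, and Protocol 7.3.1 rules out formal testing. What remains is that SAP 3.8.1 and 3.2.2 together yield a crude percentage, and that choice of metric belongs in the SAP, which makes it elsewhere.

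**Unequal retention is conjecture.** This stands. No passage shows that IFN-high and IFN-low subjects stay for different times. The point is conditional.

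**The larger ratios do not match the documented route.** This also stands. The steroid rule acts after 12 months, so 1.06 to 1.13 is the range it supports. A reader might take 1.14 to 1.32 as the expected bias, but that needs divergence from Day 1, for which the documents give no specific cause.

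**Sampling noise is as large.** With 240 subjects split 144 and 96 (assuming that the roughly 60% with an IFN signature in Protocol 1.1 applies here), the standard error of 23.7% against 18.1% is about 5.3 points for a gap of 5.6. After month 12 the gap is 2.6 points, about half a standard error. This limits what either metric can show, but it does not justify adding a systematic error to the noise.

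**The rate is imperfect.** Its denominator runs on after the first event, and it assumes a roughly constant hazard. If SAEs are front-loaded (assumed 20 or 30 per 100 patient-years for 6 or 12 months, then 5), the same dropout pairs from Day 1 give a rate ratio of 0.87 to 0.95 with no true difference. The rate should therefore stand beside the percentage and not replace it.

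**Conclusion.** The point holds in conditional form. As written, SAP 3.8.7 would show SAEs by IFN status without exposure adjustment, although the SAP applies that adjustment to the dose groups. If retention differs by IFN status, the longer-stay group will show the higher SAE percentage at the same underlying rate. Under the assumed rates, the spurious ratio is 1.06 to 1.13 for divergence after month 12 and 1.14 to 1.32 for divergence from Day 1. The SAP 3.8.4 rate brings it to about 0.97 to 1.00 under a constant hazard. With equal retention there is no distortion.

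Two stronger readings are not supported. One is that the SAE table will be biased: the documents do not establish different retention or its direction. The other is that TEAEs are affected to the same degree: most non-serious events are captured in year 1 only, so the effect there is small. The consequence is a descriptive table that can be misread, not a false test result. It merits a change because safety is the primary objective and the remedy is already defined in the SAP.

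**What to change.** In SAP 3.8.7, add beside the counts and percentages for IFN-high and IFN-low:

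- the exposure-adjusted subject rate per 100 patient-years from SAP 3.8.4, with the full-period window for SAEs and the first-year window for TEAEs;
- patient-years and median follow-up per subgroup;
- a sentence saying that any SAE difference between IFN groups is interpreted in light of the rates and not the percentages alone.

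Show the same columns for the ADA split, with a note that they do not resolve a separate problem: longer follow-up also gives more chance of being classed ADA positive.

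The cost is about one SAP sentence and a few table columns, using an existing formula and data already collected. A footnote should say that the rate assumes a roughly constant hazard and that its denominator is not censored at the first event.
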